6.4.1.5 On-OL Rimegepant AEs

Frequency tables of on-OL rimegepant AEs are provided for the on-OL rimegepant analysis set by SOC and PT for the following endpoints:

- AEs by worst intensity (other secondary objective #4) *
- AEs related to study drug by worst intensity

- SAEs (other secondary objective #4)
- AEs leading to study drug discontinuation (other secondary objective #4)
- Hepatic-related AEs (exploratory objective #13)
- Hepatic-related AEs leading to study drug discontinuation (exploratory objective #14)
- Potential drug abuse AEs, displayed in alphabetical order by worst intensity and PT without SOC
- Cardiovascular AEs
- Suicidality AEs
- Hypertension AEs
- Hypertension AEs for subjects with medical history of hypertension.

Frequency tables of endpoints marked with “*” are also provided by subgroup level and overall for all high-level safety subgroups of interest specified in Section 4.3.2. Results support exploratory objective #17.

6.4.1.6 Follow-Up AEs

Frequency tables of follow-up AEs are provided by SOC and PT for the follow-up safety analysis set for the following endpoints:

- AEs by worst intensity
- SAEs.

6.4.2 Laboratory Tests

Laboratory tests are analyzed using results from local laboratory tests reported on CRFs and the external central laboratory ACM Global Laboratories. TLFs display results in both Systeme Internationale (SI) and United States (US) units, if applicable.

Laboratory tests of clinical interest are collected at the following visits:

- Hematology: Screening; Baseline; DBT EOT; and Week 12/EOT
- Serum chemistry: Screening; Baseline; DBT EOT; and Week 12/EOT. Exceptions are for the following:
 - LFTs (alanine aminotransferase [ALT], aspartate aminotransferase [AST], alkaline phosphatase [ALP], total bilirubin [TBL], direct bilirubin, indirect bilirubin): Screening; Baseline; DBT EOT; Week 4; and Week 12/EOT.

The following by-subject laboratory test listings are provided for the enrolled analysis set:

- Laboratory test results using the Common Terminology Criteria for Adverse Events/ Division of Acquired Immune Deficiency Syndrome (CTCAE/DAIDS) toxicity grading scale

(SI units). The listing displays all test results over time for subjects with grade 3 to 4 laboratory test abnormalities at any time point.

- Laboratory test results using the Food and Drug Administration (FDA) toxicity grading scale (US units). The listing displays all test results over time for subjects with grade 3 to 4 laboratory test abnormalities at any time point.
- LFT values and ratios to ULN (i.e., ALT, AST, TBL and ALP) for SI units. The listing displays all LFT results over time for subjects with select LFT elevations (ALT or AST >3x ULN; ALP or TBL >2x ULN) at any time point.
- Pregnancy test results (SI units). The listing displays all test results over time for subjects with positive pregnancy tests at any time point.

Refer to the protocol for laboratory tests of clinical interest. Refer to the Core SAP for toxicity grades and TLF contents.

6.4.2.1 Laboratory Test Abnormalities

Frequency tables of the worst (highest) laboratory test abnormality for each graded laboratory test are provided for the following safety analysis periods and analysis sets:

- On-DBT for the DBT safety analysis set
- On-DBT for the DBT safety analysis set by subgroup level and overall for all high-level safety subgroups of interest described in Section 4.3.2 for each treatment group. Results support exploratory objective #17.
- Post-DBT pre-OL rimegepant for the interim safety analysis set
- On-OL rimegepant for the OL rimegepant safety analysis set
- On-OL rimegepant for the OL rimegepant safety analysis set by subgroup level and overall for all high-level safety subgroups of interest specified in Section 4.3.2. Results support exploratory objective #17.
- Follow-up for the follow-up safety analysis set.

Grade 3 to 4 results support other secondary objective #4.

Frequency tables of laboratory test shift from baseline to the worst abnormality for each graded laboratory test are provided for the following safety analysis periods and analysis sets:

- On-DBT for the DBT safety analysis set
- On-OL rimegepant for the OL rimegepant safety analysis set.

Separate tables are provided for each toxicity grading scale: CTCAE/DAIDS using SI units; and FDA using US units.

6.4.2.2 Liver Function Test Elevations

Analysis use SI units.

LFT Elevations

Frequency tables of LFT elevations are provided for the following analysis periods and analysis sets:

- On-DBT for the DBT safety analysis set
- Post-DBT pre-OL rimegepant for the interim safety analysis set
- On-OL rimegepant for the OL rimegepant safety analysis set
- Follow-up for the follow-up safety analysis set.

Results support exploratory objective #16.

LFT Shifts From Baseline to Worst Elevation

Frequency tables of LFT shift from baseline to the worst (highest) elevation are provided for the following safety analysis periods and analysis sets:

- On-DBT for the DBT safety analysis set
- On-OL rimegepant for the OL rimegepant safety analysis set.

LFT Plots

Evaluation of drug-induced serious hepatotoxicity (eDISH) scatter plots are provided for the following safety analysis periods and analysis sets:

- On-DBT for the DBT safety analysis set by treatment group
- On-OL rimegepant for the OL rimegepant safety analysis set by treatment group/OL rimegepant.

By-subject LFT line plots are provided for the safety analysis set with select LFT elevations in any safety analysis period. Study weeks are defined as study day/7, where study day is derived from the laboratory test collection date (see Section 7.3). Each figure also displays DB study drug and OL rimegepant dosing days using symbols along the x-axis, and denotes additional study milestones (e.g., start of the on-DBT safety analysis period, start of the on-OL rimegepant safety analysis period, and start of the follow-up safety analysis period) using vertical lines with their corresponding descriptions in footnotes. Study drug dosing days are days on which study drug was taken, i.e., nonmissing study drug date.

6.4.2.3 Laboratory Test Changes From Baseline Over Time

The table of values and changes from baseline in all hematology and serum chemistry laboratory tests is provided by treatment group and overall for the safety analysis set at the following time points: baseline; EOT in the on-DBT safety analysis period; Week 4 (LFTs only), Week 12, and EOT in the on-OL rimegepant safety analysis period. Results for overall are displayed only at baseline and time points in the on-OL rimegepant safety analysis period.

Note that scheduled visits vary according to laboratory test.

A separate table is provided for each unit system (SI or US).

Refer to the Core SAP for (1) handling multiple values in an analysis visit window or on the same laboratory test collection date, and (2) deriving the EOT value in an on-treatment safety analysis period.

6.4.3 Vital Signs and Physical Measurements

Vital signs include systolic blood pressure, diastolic blood pressure, heart rate, temperature, and respiratory rate. Physical measurements include height, weight, and BMI. These parameters are measured at all visits, except that height is measured only at the Screening Visit.

Refer to the Core SAP for TLF contents.

BMI is derived as (weight in kg)/(baseline height in m²) at all time points that weight is collected, where baseline height is derived as per Section 6.2.5.

6.4.3.1 Vital Sign and Physical Measurement Changes From Baseline Over Time

The table of values and changes from baseline in vital sign and physical measurement parameters is provided by treatment group and overall for the safety analysis set at the following time points: baseline; EOT in the on-DBT safety analysis period; each scheduled visit through Week 12 and EOT in the on-OL rimegepant safety analysis period; and Follow-up Week 2 in the follow-up safety analysis period. Results for overall are displayed only at baseline and time points during the on-OL rimegepant safety analysis period.

The table of values and changes from baseline in vital sign parameters is also provided for the safety analysis set with medical history of hypertension.

Refer to the Core SAP for (1) handling multiple values in an analysis visit window or on the same measurement date, and (2) deriving the EOT value in an on-treatment safety analysis period.

6.4.3.2 Vital Sign and Physical Measurement Abnormalities

Frequency tables of vital sign and physical measurement abnormalities are provided for the following safety analysis periods and analysis sets:

- On-DBT for the DBT safety analysis set
- On-OL rimegepant for the OL rimegepant safety analysis set
- Follow-up for the follow-up safety analysis set.

Frequency tables of vital sign abnormalities are provided for the following safety analysis periods and analysis sets:

- On-DBT for the DBT safety analysis set with medical history of hypertension

- On-OL rimegepant for the OL rimegepant safety analysis set with medical history of hypertension.

6.4.4 *Electrocardiograms*

ECG parameters include RR, QRS, PR, QT, QTcF, and ventricular heart rate. ECGs are measured by the external source Clario at the following visits: Screening; DBT EOT; OLE Week 12/EOT.

Refer to the Core SAP for TLF contents.

6.4.4.1 *ECG Changes From Baseline Over Time*

The table of values and changes from baseline in ECG parameters is provided by treatment group and overall for the safety analysis set at the following time points: baseline; EOT in the on-DBT safety analysis period; Week 12 and EOT of the on-OL rimegepant safety analysis period. Results for overall are displayed only at baseline and time points in the on-OL rimegepant safety analysis period.

Refer to the Core SAP for (1) handling multiple values in an analysis visit window or on the same measurement date, and (2) deriving the EOT value in an on-treatment safety analysis period.

6.4.4.2 *ECG Abnormalities*

Frequency tables of ECG abnormalities are provided for the following safety analysis periods and analysis sets:

- On-DBT for the DBT safety analysis set
- On-OL rimegepant for the OL rimegepant safety analysis set.
- Follow-up for the follow-up safety analysis set.

ECG abnormalities are presented together with vital sign and physical measurement abnormalities in the same frequency tables (see Section 6.4.3.2).

6.4.5 *C-SSRS*

The C-SSRS is a clinician administered questionnaire used to help immediate risk of suicide. The C-SSRS is administered at the following visits: Screening; Baseline; DBT EOT; OLE Weeks 4 and 12/EOT. At the Screening Visit, the recall period for completing is (1) 12 months and lifetime for suicidal ideation and (2) 10 years and lifetime for suicidal behavior; at all other visits, the recall period for completing the C-SSRS is since the last visit.

Frequency tables of C-SSRS suicidality are provided for the following safety analysis periods and analysis sets:

- On-DBT for the DBT safety analysis set

- On-OL rimegepant for the OL rimegepant safety analysis set.

Refer to the Core SAP for calculation of C-SSRS parameters and TLF contents. Responses to lifetime questions at the Screening Visit are excluded from analyses.

6.4.6 Safety Narrative Subject Identifiers

The by-subject listing of safety narrative subject identifiers is provided for the following select events as columns:

- Death in any analysis period for the enrolled analysis set
- SAE on DB or OL rimegepant or during follow-up for the DB or OL rimegepant safety analysis set
- Non-SAE leading to study drug discontinuation in any analysis period for the DB or OL rimegepant safety analysis set
- Other significant non-SAE on DB or OL rimegepant or during follow-up for the DB or OL rimegepant safety analysis set:
 - Select hepatic-related AE, i.e., PT containing cirrhosis, drug-induced liver injury, hepatic failure, hepatitis, jaundice, or liver failure
 - Cardiovascular AE
 - Suicidality AE
 - Hypertension AE
 - Raynaud's phenomenon AE
- LFT elevation on DB or OL rimegepant or during follow-up for the DB or OL rimegepant safety analysis set:
 - ALT or AST > 3x ULN
 - ALT or AST > 3x ULN concurrent with TBL > 2x ULN
 - ALP or TBL > 2x ULN.

Refer to the Core SAP for additional details.

6.5 Outcomes Research

Analyses are based on as-randomized treatment group for the DBT and OLE efficacy analysis sets.

Outcomes research questionnaires and rating scales are as follows:

- MQoL: 24 hours post dose after the single qualifying migraine attack in the DBT Phase and each of the first 5 qualifying migraine attacks in the OLE Phase using the eDiary
- MSQ: Baseline and Week 12/EOT using CRFs
- MIBS: Baseline; Weeks 4, 8, and 12/EOT using CRFs.

MSQ and MIBS measurements are slotted into analysis periods and analysis visits using the following steps:

1. Measurements are slotted into the pretreatment and OLE outcomes research analysis periods.
2. Measurements are slotted into the analysis visits (Weeks 4, 8, and 12) in the OLE outcomes research analysis period (see Table 6).

Refer to the Core SAP for the following: detailed descriptions of these questionnaires and rating scales; calculating scores and imputing missing data; deriving categories; handling multiple questionnaires or rating scale values in an analysis visit window or on the same assessment date; and TLF contents.

6.5.1 MQoL

Impact of treatment on patient-reported quality of life is assessed using the MQoL Version 3.0, which is a 16-item questionnaire that has been validated in migraine patients to measure the short-term impact of treatment within 24 hours. The MQoL consists of 15 items across the following 5 domains: (1) work functioning; (2) social functioning; (3) energy/vitality; (4) migraine symptoms; (5) feelings/concerns. Item (Question) 16 measures overall change in migraine symptoms since taking study medication. See Section 7.4.4 for additional details.

6.5.1.1 Reliability of Rimegepant Effect in the OLE Phase

Reliability of rimegepant effect in the OLE Phase is assessed using the proportions of subjects achieving response after (1) the single EQMA in the DBT Phase (i.e., π_{DBT}) for the DBT efficacy analysis set randomized to rimegepant, and (2) each of the first 5 EQMAs ≥ 23 hours apart in the OLE Phase (i.e., $\pi_{\text{OLE}i}$, $i = 1, \dots, 5$) for the OLE efficacy analysis set.

An EQMA is defined as a qualifying migraine attack (see Section 6.3.5.5) with a nonmissing MQoL Question 16 value at 24 hours postdose.

Reliability of rimegepant effect in the OLE Phase is defined as percentages for ≥ 4 of the first 5 EQMAs ≥ 23 hours apart in the OLE Phase being no more than 7% less than the percentage in the DBT Phase, i.e., $\pi_{\text{DBT}} - \pi_{\text{OLE}i} \leq 7\%$ for ≥ 4 of the 5 $\pi_{\text{OLE}i}$.

Response is defined as a category (value) of “moderately better” or “very much better” for MQoL Question 16 (overall change in migraine symptoms since taking study medication) at 24 hours postdose.

For a given EQMA, subjects who meet all the following criteria are classified as responders:

- MQoL Question 16 value of “moderately better” or “very much better” at 24 hours postdose, i.e., in the 24-hour postdose analysis window
- No rescue medication taken at or before the MQoL Question 16 value in the 24-hour postdose analysis window (see Section 7.5)

- **No intervening OL rimegepant taken at or before** the MQoL Question 16 value in the 24-hour postdose analysis window (see Section 7.7). This applies only to MQoLs in the OLE Phase.

For a given EQMA, subjects who are not responders are classified as failures. Failure criteria include any of the following:

- Rescue medication taken at or before the MQoL Question 16 value in the 24-hour postdose analysis window (RM=F; see Section 7.5)
- **Intervening OL rimegepant taken at or before** the MQoL Question 16 value in the 24-hour postdose analysis window (Intervening OL Rimegepant = Failure [IOL=F]; see Section 7.7). This applies only to MQoLs in the OLE Phase.
- MQoL Question 16 value of “A little better”, “No change”, “A little worse”, “Moderately worse” or “very much worse” at 24 hours postdose.

Thus, for a given EQMA, subjects with missing MQoL Question 16 value at 24 hours postdose are excluded, i.e., missing MQoL Question 16 data are not imputed. For a given EQMA, the percentage is calculated against the number of evaluable subjects, i.e., those defined as responders or failures.

For the single EQMA in the DBT Phase, analyses are based on the DBT efficacy analysis set randomized to rimegepant with EQMA and MQoL eDiary measurement dates in the DBT Phase analysis period.

For the first 5 EQMAs ≥ 23 hours apart in the OLE Phase, analyses are based on the OLE efficacy analysis set with EQMA and MQoL eDiary measurement dates in the OLE outcomes research analysis period.

The RM=F algorithm (criterion 1 only) is applied to the single EQMA in the DBT Phase, and to the first 5 EQMAs ≥ 23 hours apart in the OLE Phase. For a given EQMA, subjects who take rescue medication at or before the MQoL measurement at 24 hours post dose are classified as failures.

The IOL=F algorithm is applied only to the first 5 EQMAs ≥ 23 hours apart in the OLE Phase. For a given EQMA, subjects who take intervening OL rimegepant at or before the MQoL measurement at 24 hours post dose are classified as failures.

See Section 9.3.1 for additional details.

Table of Reliability of Rimegepant Effect

The table of reliability of rimegepant effect displays the following for each EQMA by overall:

- Response rate (i.e., “n/N” and percentage; π_{DBT} , π_{OLEi} , $i = 1, \dots, 5$), ASE, and 95% CI. For a given EQMA, the percentage is calculated against the number of evaluable subjects (“N”), i.e., those defined as responders or failures.

- Percentage difference $\pi_{\text{DBT}} - \pi_{\text{OLE}i}$ for each EQMA in the OLE Phase. Percentage differences $<7\%$ are identified.

A footnote defines the reliability of rimegepant effect, and states whether it was achieved. CIs are based on the normal approximation to the binomial distribution.

Results support other secondary objective #1.

The table of reliability of rimegepant effect is also produced using the first 5 EQMAs ≥ 47 hours apart in the OLE Phase as a sensitivity analysis.

Frequency Table of MQoL Overall Change in Migraine Symptoms Outcomes by EQMA

The frequency table of MQoL overall change in migraine symptoms (Question 16) outcomes displays the number and percentage of subjects by treatment group/OL rimegepant and overall in the following categories and subcategories at each EQMA:

- Responder (π_{DBT} , $\pi_{\text{OLE}i}$, $i=1, \dots, 5$)
 - Moderately better
 - Very much better
- Failure
 - Rescue medication taken at or before the MQoL Question 16 value at 24 hours postdose (RM=F)
 - Intervening OL rimegepant taken at or before the MQoL Question 16 value at 24 hours postdose (IOL=F). This subcategory applies only to MQoLs in the OLE Phase.
 - Very much worse
 - Moderately worse
 - A little worse
 - No change
 - A little better.

Subjects may be in either or both RM=F or IOL=F subcategories, but can only be in 1 of the last 5 failure subcategories (very much worse, ..., a little better).

For a given EQMA, percentages are calculated against the number of evaluable subjects, i.e., those defined as responders or failures.

The frequency table of MQoL overall change in migraine symptoms outcomes is also produced using the first 5 EQMAs ≥ 47 hours apart in the OLE Phase as a sensitivity analysis.

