9.3.1.2. Secondary Endpoints

The same statistics for key secondary endpoints during the DBT Phase (i.e., those listed in [Section 3.2.1](#)) will be presented as those for the primary endpoint.

For endpoints based on a single time point during the DBT Phase, such as migraine headache pain freedom at 2 hours postdose, subjects with missing data at a single time point will be classified as failures.

For endpoints based on multiple time points during the DBT Phase, such as sustained migraine headache pain relief from 2 to 48 hours postdose, subjects with missing data at (1) 2, 24, or 48 hours postdose, or (2) more than 1 time point from 3 to 8 hours postdose will also be classified as failures.

Reliability of rimegepant effect during the OLE Phase will be assessed using the percentages of subjects achieving response after (1) the single evaluable qualifying migraine attack in the DBT Phase (i.e., π_{DBT}) for the DBT efficacy analysis set randomized to rimegepant, and (2) each of the first 5 evaluable qualifying migraine attacks ≥ 23 hours apart in the OLE Phase (i.e., $\pi_{\text{OLE}i}$, $i = 1, \dots, 5$) for the OL rimegepant efficacy analysis set.

- Reliability of rimegepant effect during the OLE Phase is defined as percentages for ≥ 4 of the first 5 evaluable qualifying migraine attacks ≥ 23 hours apart in the OLE Phase being no more than 7% less than the percentage in the DBT Phase, i.e., $\pi_{\text{DBT}} - \pi_{\text{OLE}i} \leq 7\%$ for ≥ 4 of the 5 $\pi_{\text{OLE}i}$. The cutoff of 23 hours aligns with the lower bound of the 24-hour postdose analysis window for eDiary MQoL data collection.
- Response is defined as a category of “moderately better” or “very much better” for MQoL Question 16 (overall change in migraine symptoms since taking study medication) at 24 hours postdose.
- An evaluable qualifying migraine attack is defined as a qualifying migraine attack (see [Section 4.1](#)) with a nonmissing MQoL Question 16 category at 24 hours postdose.

The percentages of subjects achieving response will be presented descriptively using “n/N” and 95% CI by evaluable qualifying migraine attack.

A frequency table will display the number and percentage of subjects in each MQoL Question 16 category (plus additional categories for RM=F and IOL=F) by evaluable qualifying migraine attack.

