2 STUDY DESCRIPTION

2.1 Study Design

C4951004 is a multicenter, Phase 4, randomized, double-blind placebo-controlled study, with an Open-Label Extension (OLE) Phase to assess the efficacy and tolerability of rimegepant for the acute treatment of migraine in subjects who are unsuitable for triptan use.

[figure not shown]
The study has 4 phases:

- Screening Phase: Lasts up to 28 days and includes the Screening Visit.
- DBT Phase:
 - Includes the Baseline Visit at which randomization occurs, and DBT EOT Visit.

- Subjects are randomized 1:1 to rimegepant orally dissolving tablet (ODT) 75 mg or matching placebo.
- Randomization is stratified using a Randomization and Trial Supply Management (RTSM) system by history of clinically relevant cardiovascular (CV) disease (yes or no). See Section 2.2.
- After randomization, 1 tablet of study medication is dispensed to subjects to take home for up to 45 days.
- Subjects are instructed by an electronic diary (eDiary) to take 1 tablet of study drug after a migraine attack of moderate or severe headache pain intensity.
- Subjects return to the study site for the DBT EOT Visit either (1) within 7 (\pm 2) days after taking study drug, or (2) within 45 days after randomization otherwise.
- OLE Phase:
 - Subjects who complete the DBT Phase and continue to meet all inclusion/exclusion criteria may enter the OLE Phase, pending review of laboratory test results at the DBT EOT Visit.
 - Subjects may take up to 1 tablet of open-label ODT rimegepant 75 mg per calendar day as needed for acute treatment of migraine for a maximum of 18 doses per month (month is 28 days).
 - Lasts up to 12 weeks, and includes the Week 2, Week 4, Week 8, Week 12, and OLE EOT Visits.
 - All subjects who discontinue early from the OLE Phase should complete the OLE EOT Visit. Otherwise, subjects should complete the Week 12 Visit.
- Follow-Up Phase
 - Lasts up to 2 weeks, and includes the Follow-Up Week 2 Visit primarily for safety assessments. This visit should occur approximately 2 weeks after the Week 12 or OLE EOT Visit.
 - All subjects who enter the OLE Phase should complete the Follow-Up Week 2 Visit (regardless of completing the OLE Phase), except those who discontinue early from the OLE Phase due to withdrawal by subject or lost to follow-up.

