5 SAMPLE SIZE, POWER, AND TYPE I ERROR

It is anticipated that about 90% of the 300 subjects randomized to each treatment group will have a migraine in the allotted time period of the DBT Phase, resulting in approximately 270 subjects evaluable for efficacy in each treatment group.

The sample size calculation is based on pooled results from Phase 3 single-dose migraine studies C4951054 (BHV3000-301), C4951055 (BHV3000-302), and C4951056 (BHV3000-303). Pooled response rates for migraine headache pain relief at 2 hours postdose were 57.9% for rimegepant 75 mg and 43.9% for placebo in these studies.

A total sample size of 540 evaluable subjects (270 per treatment group) will provide approximately 90% power for the primary endpoint of migraine headache pain relief at 2 hours postdose in the DBT Phase. This is based on a chi-square test with a 2-sided alpha level of 0.05, and assumes that the true response rates in the subjects unsuitable for triptan use is equivalent to the overall pooled response rates above.

Type 1 error is controlled using a 2-sided alpha level of 0.05 and hierarchical testing. First, the significance of the primary endpoint is evaluated at the 2-sided alpha level of 0.05 for rimegepant versus placebo. If the primary endpoint is not significant (i.e., $p\text{-value} > 0.05$), then any further tests on key secondary endpoints will have p-values presented only for descriptive purposes. If the primary endpoint is significant (i.e., $p\text{-value} \leq 0.05$), then the key secondary endpoints are tested hierarchically, each at a 2-sided alpha level of 0.05, in the order specified in Section 3.2.2.1. Thus, a key secondary endpoint is tested only if the preceding key secondary endpoint in the hierarchy is determined to be significant (i.e., $p\text{-value} \leq 0.05$). If a test in the hierarchy is not significant, then any further tests on endpoints in the sequence have p-values presented only for descriptive purposes, and no conclusions are drawn from those results.

For testing of other secondary or exploratory endpoints, no attempt is made to adjust for multiplicity. P-values are evaluated at an unadjusted, 2-sided alpha level of 0.05 and presented only for descriptive purposes.

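### The reliability verdict compares point estimates from overlapping but different groups, plans no interval for the difference, and uses a table flag that does not match the rule

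*SAP*

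**What the plan says.** Reliability of effect is the first of the other secondary objectives. It uses Question 16 of the MQoL questionnaire at 24 hours, at evaluable qualifying migraine attacks (EQMAs).

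- **Groups.** SAP 6.5.1.1 takes the DBT percentage "for the DBT efficacy analysis set randomized to rimegepant, and (2) each of the first 5 EQMAs" at least 23 hours apart come from the OLE efficacy set. SAP 4.1 defines that set as DBT efficacy subjects of either arm who took at least one open-label dose. The reliability table shows the arms pooled.
- **Denominator.** "For a given EQMA, the percentage is calculated against the number of evaluable subjects, i.e., those defined as responders or failures". A missing Question 16 value is excluded, not imputed.
- **What counts as an attack.** Under SAP 9.3.1 the attack must be treated first with study drug. A subject who has stopped can supply no further attack, although SAP Table 3 labels discontinuation as treatment policy for this objective.
- **Rule.** Protocol 9.3.1.2 requires at least four of the five OLE percentages to satisfy "being no more than 7% less than the percentage in the DBT Phase". SAP 6.5.1.1 repeats this as a difference of at most 7%.
- **Reporting.** Each response rate gets a 95% confidence interval; the difference gets none. The table marks differences strictly below 7%. "A footnote defines the reliability of rimegepant effect, and states whether it was achieved". The only sensitivity analysis of the verdict changes the spacing to 47 hours.

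**The concern.** The objective asks whether the effect seen at the blinded attack holds over later attacks. The planned comparison can move for three other reasons.

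1. The people change. The DBT group includes rimegepant subjects who never enter the OLE, and each later OLE percentage rests on a smaller remaining group. If subjects tend to stop after a failed attack, that remaining group is enriched for responders.
2. Sampling error is ignored. A yes/no statement is made from five observed differences, none shown with its uncertainty.
3. At a difference of exactly 7% the rule is met but the table does not mark it.

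At stake is a labelled conclusion in the study report. A loss somewhat beyond the allowance could be reported as reliability achieved, with nothing beside it to show how uncertain that is.

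**Working it through.** **1. The plan's own figure.** SAP section 5 gives an operating figure only for the primary endpoint: "A total sample size of 540 evaluable subjects (270 per treatment group) will provide approximately 90% power", at "57.9% for rimegepant 75 mg and 43.9% for placebo" with a "chi-square test with a 2-sided alpha level of 0.05". The pooled rate is (0.579 + 0.439)/2 = 0.509, so power = Φ{[0.14·√270 − 1.96·√(2·0.509·0.491)] / √(0.579·0.421 + 0.439·0.561)} = Φ{(2.300 − 1.386)/0.700} = Φ(1.307) = 90.4%. It reproduces. No error rate or justification is given for the 7-point rule.

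**2. Precision of one difference.** Inputs: about 270 evaluable rimegepant subjects (SAP 5) and about 510 OLE entrants (Protocol 5.1). The Question 16 response rate is not stated; 60% is assumed. At a true 8-point loss, and treating the groups as independent, the half-width is 1.96·√(0.60·0.40/270 + 0.52·0.48/510) = 1.96·0.0371 = 7.3 points. Over 50 to 70% response it runs from 6.9 to 7.4. Overlap between the groups narrows it a little. One difference is therefore known to about the size of the allowance itself.

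**3. Chance of meeting the rule.** The SAP rule was simulated with 270 DBT subjects and 510 OLE subjects, half of the latter from each arm. Subjects have a latent-normal effect, and the same true loss applies at every OLE attack. Leaving is modelled as a chance of stopping after each failed attack. Loss, correlation and leaving rates are assumptions.

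| True loss | No failure-driven leaving | 10% leave after each failure | 20% leave |
|---|---|---|---|
| 0 | 97% or more | 99% | over 99% |
| 8 points | about 24–27% | 37–40% | 49–54% |
| 10 points | about 10% | 17–18% | 28–30% |
| 12 points | 2–3% | 5–6% | 10–12% |

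The two right-hand columns use correlation 0.4 and span 50 to 70% response.

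**4. Drift from leaving alone (large sample, 60% response, correlation 0.3 to 0.4, no true loss).** The attack-5 percentage rises about 2 to 2.5 points with 10% leaving after each failure, and about 4 to 5 with 20%. The 20% scenario is heavy. Ignoring correlation, each attack removes 0.40 × 0.20 = 8% of subjects, so 1 − 0.92⁴ = 28% are gone by attack 5.

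At correlation 0.4 and 20% leaving, a constant true 8-point loss appears as 8.0, 6.6, 5.1, 3.7 and 2.3 points. Four of five fall within 7, so the rule is met however large the trial. A true 10-point loss appears as 10.1, 8.4, 7.0, 5.7 and 4.2. At most three are within 7, so in a large sample the rule is not met.

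**5. Flag against rule.** At a difference of exactly 7%, the rule (at most 7%) is satisfied and the table mark (below 7%) is absent.

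**The case against.** The best defence has several parts, and most of it stands.

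- The endpoint is an other secondary outside the testing hierarchy. Protocol 9.3.1.2 presents the percentages descriptively, and Protocol 1.3.1 aims at consistency at the population level. Trial type I error is not touched.
- An answered attack on which the drug fails is counted: a lesser Question 16 category, rescue use or intervening rimegepant each makes a failure at that attack. Protocol 4.1 keeps collecting the questionnaire until five are completed. Only attacks after stopping are lost.
- About 510 of 540 evaluable subjects (94%) are expected to enter the OLE, so selection at entry is limited.
- A reader might infer that pooling former placebo subjects biases the comparison. It does not in itself, because "Subjects are randomized 1:1 to rimegepant orally dissolving tablet (ODT) 75 mg or matching placebo" makes the arms alike apart from chance.
- Subjects may also fall short of five attacks because they have few, which could act in the other direction.
- Other outputs help: the Question 16 frequency table is split by former arm, the mixed model uses all OLE attacks, and reasons for not completing the OLE are tabulated.

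What remains is that none of these outputs puts an interval on the difference, compares the same people across phases, or alters the footnote's statement.

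**Conclusion.** The concern holds in a limited form. The mechanism is in the text: changing groups, no attack counted after stopping, a yes/no statement from point estimates, and a flag that disagrees with the rule. The risk matters for true losses just beyond the allowance, at 8 to 10 points. It is small at 12 points or more unless failure-driven leaving is heavy. All sizes depend on assumed response, correlation and leaving rates.

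Two stronger readings are not supported.

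- A reader might infer that ordinary attrition fills most of the 7-point allowance. Treating response as a fixed trait, with 30% of non-responders and 10% of responders gone by attack 5, gives 0.6·0.9/(0.6·0.9 + 0.4·0.7) = 65.9%, a rise of 5.9 points. That assumes every leaver's later response is already known. With correlation 0.3 to 0.5 the same attrition gives about 1 to 2 points, and the documents state no drop-out rate from which to argue for more. Attack 5 may also miss without failing the rule.
- A reader might count as an error the roughly 36 to 39% of trials that meet the rule at a true 7-point loss. A 7-point loss is within the margin, so meeting the rule there is not a false conclusion.

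**What to change.** Keep the protocol rule and make four changes in SAP 6.5.1.1.

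1. Mark differences of at most 7%, to match the rule.
2. Add a 95% confidence interval for each DBT-minus-OLE difference and report it beside the footnote verdict. Use a subject-level bootstrap, because the groups overlap.
3. Add one sensitivity table. For each attack i, compare rimegepant-randomized subjects evaluable at that attack with their own DBT response, giving the paired difference and 95% confidence interval. Do not use a cohort that must have all five OLE attacks, since it is selected on OLE outcomes. At correlation 0.3 and 20% leaving it shows about 3.5 points at attacks 1 to 4 for a true 8-point loss, whereas attack-by-attack pairing recovers about 8 at every attack.
4. Have the footnote call the verdict descriptive and cite the paired result.

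The cost is SAP wording and one extra table from data already collected. The paired table has a smaller N (at most about 510/2 = 255 if entry is even between arms) and wider intervals. It does not recover outcomes after stopping, does not remove the contrast between blinded and open-label rating, and would itself tilt if entry to the OLE depended on the DBT response.
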